12.4 Analysis of secondary endpoints

SARS-CoV2 Log₁₀ viral loads at follow-up timepoints will be compared between groups using the Wilcoxon rank-sum test and/or generalized estimating equations with robust standard errors. The area-under-the-curve (AUC) SARS-CoV2 viral RNA levels during follow-up will be estimated using the linear trapezoidal method, and mean AUC levels compared between groups using the Wilcoxon rank-sum test.

The distribution of cessation of symptoms will be estimated using the Kaplan-Meier method, and Kaplan-Meier curves will be presented for each treatment arm. Time to cessation of symptoms at the end of the study period along with 95% confidence intervals will be presented for each treatment arm. The hazard ratio for cessation of symptoms will be estimated, along with its 95% confidence intervals, from a Cox proportional hazards model. Time to cessation of symptoms will be estimated in the subgroup of patients who are symptomatic at baseline.

The incidence of hospitalizations and emergency department visits will be compared between groups using negative binomial regression models, which will account for differing follow-up times through an offset term.

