### 1.3 Secondary endpoints

Secondary endpoints include the following:

- Time until resolution of all symptoms;
- SARS-CoV-2 viral load over time in oropharyngeal tests;
- SARS-CoV-2 viral load area under the curve in oropharyngeal tests through Day 14;
- Number of emergency department visits or hospitalizations within 28 days of treatment.

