### **2.4 Secondary efficacy analyses**

Time to resolution of all symptoms will be defined as the time from randomization until the first study day in which no symptoms are reported. The distribution of time to resolution of symptoms will be estimated using the Kaplan-Meier method, and Kaplan-Meier curves will be presented for each treatment arm. Time to symptom resolution at the end of the study period along with 95% confidence intervals will be presented for each treatment arm. The hazard ratio for resolution of symptoms will be estimated, along with its 95% confidence intervals, from a Cox proportional hazards model adjusted for age and sex.

We will model SARS-CoV-2 viral load in oropharyngeal tests over time using a generalized mixed effects linear regression model with a random effect for study participant to account for correlation within a participant. Viral load with cycle threshold (Ct) values above the limit of detection will be calculated by substituting a Ct value of 42 into the equation  $10^{(Ct - 42) * 0.23}$  to derive viral load from Ct. A logarithmic transformation on viral load will be fit to treatment arm, time, armXtime, and adjusted for age and sex to account for therandomization stratification variables. The armXtime interaction term will allow us to assess whether the trajectory of viral load differs by treatment arm. Time will be defined as days from randomization and, depending on model fit, will either be modeled continuously or with a flexible approach allowing a non-linear trajectory for the change in viral load over time. Model fit will be assessed based on visual inspection of the residuals. Alternative transformations or generalized linear models with a link function besides the identity link will be considered if the model does not fit the data well.

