Area under the curve (AUC) will be defined by a single participant's logarithmic base 10 viral load from oropharyngeal tests collected on days 0, 1, 3, 5, 7, 10, and 14. AUC will be calculated by the trapezoidal rule, using exact times of collection of each OP swab. Multiple imputation using chained equations will be used to impute missing viral load data prior to AUC calculation. Five data sets will be imputed, and imputed values will be calculated using non-missing viral load on each of the 7 sample collection days, treatment arm, age, sex, and whether or not a participant was hospitalized. A pooled linear regression model will be fit to log-transformed AUC as a function of treatment, age, and sex using the 5 imputed data sets. Difference in AUC by treatment arm and corresponding 95% confidence intervals will be reported using Rubin's Rules. The difference in AUC by treatment arm will also be done after refitting the model without participants who were hospitalized to assess sensitivity of results.

The incidence of hospitalizations and emergency department visits will be estimated for each arm, with 95% confidence intervals.

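### Protocol 12.4 and SAP 2.4 prescribe different analyses for the two viral-load secondary endpoints, and neither document says which governs

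*Protocol*

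**What the plan says.** **Viral load over time.** Protocol 12.4 compares log10 loads at follow-up timepoints "using the Wilcoxon rank-sum test and/or generalized estimating equations with robust standard errors". It names no timepoint. Protocol 9.1.2 schedules eight follow-up swab visits (Days 1, 3, 5, 7, 10, 14, 21 and 28). SAP 2.4 models oropharyngeal load "using a generalized mixed effects linear regression model with a random effect for study participant", adjusted for age and sex, and adds: "The armXtime interaction term will allow us to assess whether the trajectory of viral load differs by treatment arm".

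**AUC.** Protocol 12.4 takes AUC by the linear trapezoidal method during follow-up, with "mean AUC levels compared between groups using the Wilcoxon rank-sum test". SAP 1.3 defines the endpoint as "SARS-CoV-2 viral load area under the curve in oropharyngeal tests through Day 14". SAP 2.4 imputes missing loads by chained equations (five data sets) and then states: "A pooled linear regression model will be fit to log-transformed AUC as a function of treatment, age, and sex". It reports the difference between arms with a 95% confidence interval.

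**Significance level.** SAP 2.2 sets 0.05 for all tests unless otherwise noted. The protocol states a level only for the primary comparison (12.3 and 12.6).

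**Relation between the documents.** The SAP revision history says version 2.0 was updated to match Protocol version 3, with details added on statistical methods and missing data. Neither document contains a precedence rule.

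**The concern.** A reader holding both documents cannot tell which analysis of viral load or AUC was pre-specified. The two sets differ in test, covariate adjustment and handling of missing swabs and, as far as the protocol's open wording shows, in time window. An adjusted, imputed regression replaces an unadjusted rank test; it does not fill in its details. If the results fall on either side of 0.05, either could be presented as the planned one.

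Reducing viral load is part of the second objective in the protocol synopsis, and these are two of the secondary efficacy endpoints in Protocol 5.2. In a phase 2 antiviral trial, readers will give them weight.

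**Working it through.** **1. The texts side by side**

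| | Protocol 12.4 | SAP 1.3 and 2.4 |
|---|---|---|
| Load over time: method | Wilcoxon and/or GEE | Mixed model, arm-by-time term |
| Load over time: adjustment | None stated | Age, sex |
| AUC: window | During follow-up, no end day | Days 0 to 14 |
| AUC: method | Wilcoxon | Linear regression on log-transformed AUC |
| AUC: adjustment | None | Age, sex |
| AUC: missing swabs | Not stated | Multiple imputation |
| Specimen | Not stated | Oropharyngeal (nasal is exploratory, SAP 1.4) |

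The protocol's and/or leaves the viral-load test open even without the SAP.

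**2. Bounds on the error from a free choice**

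The documents give no operating characteristic for these endpoints, so there is no figure to reproduce. For two tests at 0.05, the chance under no effect that at least one is significant is at most 0.05 + 0.05 = 0.10. It would be 1 - 0.95² = 0.0975 if they were independent. Tests on the same swabs are correlated, so the true value is lower.

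**3. Simulation, no treatment effect**

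From the documents: 60 per arm and the visit days. Assumed: mean log10 load of 5 at baseline, a linear decline to a floor of 0, and complete data.

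- *AUC.* Wilcoxon to Day 28 against age- and sex-adjusted regression of log AUC to Day 14; 10,000 trials in each of three scenarios (median decline 0.45, 0.35 or 0.20 log10 per day). Loads were generated as zero or positive, so the formula problem in step 5 does not arise. Each test alone rejected in 4.7% to 5.0% of trials. At least one rejected in 6.7%, 6.4% and 7.0%.
- *By-visit Wilcoxon, eight visits.* At least one below 0.05 in about 21% of 2,000 trials (median decline 0.35 per day, noise SD 0.8). With baseline SD 1.5, decline 0.5 ± 0.2 per day and noise SD 1 (3,000 trials), one run gave 22% and a repeat gave 24%.
- *Across the documents, load over time.* GEE main effect or arm-by-time test, both in unadjusted balanced-data approximations: 9.2% (2,000 trials).

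The by-visit figure measures the choice left inside Protocol 12.4. The 9.2% and the AUC figures measure the conflict between the two documents.

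**4. Simulation, 25% steeper decline in the treated arm**

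Using the 0.5 ± 0.2 inputs and 1,500 trials, a t-test on AUC to Day 14 and a Wilcoxon test on AUC to Day 28 disagreed on significance in 11% of trials in one run and 9% in a repeat. With both tests cut at Day 14, disagreement was still about 9%. Most of it therefore comes from the test and little from the window.

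**5. Can the SAP's models be adopted as they stand?**

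SAP 2.4 prints load as 10 to the power (Ct - 42) × 0.23, so log10 load = (Ct - 42) × 0.23:

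- Ct 20: (-22) × 0.23 = -5.06
- Ct 30: (-12) × 0.23 = -2.76
- Ct 42 (undetected): 0

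Log10 load is zero or negative for every Ct up to 42. The AUC of log10 load is then zero or negative, and its logarithm is undefined. With the sign reversed, a participant undetectable at every visit still has AUC 0, whose logarithm is also undefined.

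For viral load over time, SAP 2.4 lets the form of time depend on fit, judges fit by visual inspection of residuals, and allows other transformations or link functions. That is not yet a single test.

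**The case against.** The best reply is that the SAP is plainly the operative text. Its introduction calls it a comprehensive and detailed account of the techniques to be used, and its revision history records added methods detail. On that view Protocol 12.4 is a summary that was not updated. This is a reasonable guess at intent, and the mismatch may be no more than an alignment lapse. But it falls short of a precedence rule, and the same history says the SAP was updated to match the protocol, which on these endpoints it does not.

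Three further objections stand and limit the point.

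- A reader might infer that both documents fix 5% for these tests and that this level is breached. They do not. The protocol's level belongs to the primary comparison, and the SAP's 0.05 covers the SAP's tests, which include neither the Wilcoxon nor the GEE comparison of these endpoints.
- A reader might take Day 28 as the protocol's AUC window. Section 12.4 gives no end day; Day 28 comes from the visit schedule, and Day 0-14 could be read as narrowing an open term.
- A reader might infer that the protocol licenses a positive claim from any one visit. No passage says so. The wording merely fails to exclude it.

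**Conclusion.** The conflict holds on the text and does not depend on any simulation. For each of the two viral-load secondary endpoints the documents prescribe different analyses, with no statement of which governs.

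The consequence is moderate. Under no effect, free choice gives about 20-25% for any of eight by-visit Wilcoxon tests and about 6-7% for either AUC test. Under a 25% steeper decline, the AUC tests disagree on significance in about 10% of trials. These figures rest on assumed trajectories and complete data, since the documents give no viral-load variance or correlation. They show scale only. The inflation from the AUC conflict alone is small; the open by-visit choice matters more.

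It would be wrong to extend this to the trial's main result. The primary Cox analysis is worded the same in Protocol 12.3 and SAP 2.3. The point should be fixed, but it does not threaten the primary conclusion.

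**What to change.** Amend Protocol 12.4 to one analysis per endpoint and state that the SAP governs.

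- **Viral load over time:** delete the and/or and make by-visit comparisons descriptive. Use the SAP mixed model on oropharyngeal load, with one default form of time, transformation and link fixed in advance. Label any alternative a sensitivity analysis.
- **AUC:** use oropharyngeal Day 0-14 in both documents, with age- and sex-adjusted regression on the untransformed AUC of log10 load. First correct the sign of the Ct-to-load formula in SAP 2.4, and drop the log transformation of AUC.

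The cost is a few sentences in a protocol amendment and a short SAP revision. No new data are needed and no participant procedure changes. The edits should be made before the blinded statisticians see treatment assignments.

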12.5 Analysis of safety endpoints

The frequency of adverse events and serious adverse events will be tabulated by type and by treatment arm. AEs will be compared by arm using the Chi-squared test or Fisher's exact test, as appropriate, in the safety analysis set.

12.6 Sample size and randomization

For the primary comparison, the following will be tested:

- Null hypothesis: time to cessation of oral shedding is equal in control and treatment;
- Alternative hypothesis: time to cessation of oral shedding differs between control and treatment.

Hypothesis tests will be two sided and conducted at an overall alpha = 0.05 level of significance.

We assume that the mean duration of virologic shedding in individuals receiving standard of care is 14 days, with a standard deviation of 4 days¹.

Assuming 1:1 randomization and the use of a two-sided log rank test at the alpha=0.04999 level of significance for the final analysis, 79 events will provide 80% power to detect a hazard ratio of 2.03. This leaves alpha=0.00001 to check for overwhelming efficacy after 50% of participants have completed 24 hours of follow-up. Assuming the control and treatment arm median cessation of shedding is 14 and 7 days, respectively, a two-month accrual period, a two-week follow-up period after randomization of the last patient, and a drop out of 10% in the control arm, it is estimated that the total sample size required to achieve 79 events is 120 (60 patients in each arm).

As described in section 6.6 above, we provide the following power calculations showing how potential study alterations due to slow enrolment would impact the study's operating characteristics. If fewer than 10 patients have been enrolled within the first two weeks, a potential solution to increase enrollment is to change the randomization ratio to be 2:1 on treatment:control, which would reduce the chance of being randomized to placebo to 33%. Under the assumptions described above, the change in the randomization ratio will not require a larger sample size.

We also consider how a change in the standard of care could impact our study's power. If the standard of care changes and our expected effect size decreases, our expected power would decrease to 61%, 41%, or 22% under an assumed hazard ratio of 1.8, 1.6, or 1.4, respectively. The impact of the change to the standard of care will depend on what proportion of patients have been enrolled. If the standard of care changes before enrollment is 90% complete, we will estimate the conditional power based on the current enrollment and the expected decrease in the effect size; we would not look at the blinded study data or outcome data to estimate the conditional power. If the conditional power is < 70%, the study will be modified by increasing the sample size such that the conditional power reaches 80%. If the total required sample size to reach 80% conditional power is greater than 180, the study will be stopped for futility.

13. DATA COLLECTION, RETENTION AND MONITORING

13.1 Data collection instruments

Paper data (informed consent documents, screening and contact information) will be maintained in a research chart. The remaining clinical data-- daily questionnaires, case record forms (CRFs), and laboratory results--will be entered and maintained in Stanford's RedCap database using the minimum number of personal identifiers (DOB, dates of visit). Physical copies of laboratory data from point of care devices will be stored in a file. Specimen containers and blood tubes will be labeled by the clinical research coordinator only with study ID and date. Virologic measurements will be entered into a database stored on secured servers and provided from the clinical laboratory to the study team. Biobanked specimens (e.g. PaxGene, plasma, PBMC) will be entered into the Stanford Biobank database stored on secure servers.

13.2 Data management procedures

All subjects will be given a study ID. Symptom questionnaires and CRFs used at clinic visits will be completed by subjects and or study personnel using only study ID. Specimen containers will be labeled by the CRC only with study ID and date, time of collection. Virologic measurements will be provided back to the study team electronically once available, and entered into a RedCap database by a CRC.

13.3 Data quality control and reporting

In order to ensure data quality, the study CRC will perform a nightly data quality audit. For this audit all study forms entered into the data management system from that date will be assessed for accuracy with source documents. In addition, the study Data Manager will perform monthly reviews of the data management system audit trail log to identify potential data quality issues. The data will be owned by Stanford University.

13.4 Archival of data

Electronic data including all study databases and supporting electronic documentation will be archived to cloud-based servers on a daily basis.

13.5 Availability and retention of investigational records

All data will be kept in secured RedCap and Box servers. Only the research team will have access to the data.

13.6 Subject confidentiality

Participants will be asked at screening (after the consent is signed) if it is permissible for the study staff to contact them via telephone. If so, the participant's preferred telephone number will be documented in the research record. Subject identification by phone will require two pieces of personal identification (DOB and subject ID#). Computerized questionnaires via redcap are password protected, encrypted and monitored by Stanford IT.

Participant interactions (interviews, data collection, PEs, blood draws, etc.) will be completed in a private clinic room. The following health information related to this study may be used or disclosed in connection with this research study, including, but not limited to, name and initials, address, email, phone number(s), date of birth, age, sex, race, ethnicity, medical record number, information related to COVID-19 disease, symptoms, physical exams, symptoms that might relate to medication side effects, vital signs including temperature and oxygen saturation levels laboratory tests, radioimaging results, pregnancy test and tests of viral shedding of Covid-19 and other viruses, medications received including study drug, and phone call records.

All subjects will be given a sequential study ID. The code for this ID with personal identifiers will be maintained in a locked research file accessible only to study personnel. Only research personnel will have access to the research records. The data will be keyed into a secure study website in a coded fashion by the study coordinator. Paper research charts will be kept in a locked file cabinet with limited access. The study coordinator is the only one that has the key to the locked cabinet where the research charts are stored. Laboratory personnel will have access to study specimens. The data is transferred by computer via password protected electronic network. When transferring via electronic networks a password protected encrypted computer will be used.

14. ADMINISTRATIVE, ETHICAL, REGULATORY CONSIDERATIONS

14.1 Institutional review board

This study protocol, all procedures and consent forms, and any subsequent protocol amendments must be reviewed and approved by the Institutional Review Board of Stanford University.

14.2 Informed consent form

All study participants will provide written informed consent for participation in the study and future use of biologic specimens. (Appendix 2)

14.3 Publications

The findings from this study may be published in a medical journal. No individual identities will be used in any reports or publications resulting from the study. The researchers will publish results of the trial in accordance with Stanford guidelines.

Appendix 2. Schedule of Events

Appendix 3. DAIDS Toxicity Table (clarification Aug 2017)

Division of AIDS Table for Grading the Severity of ADULT AND PEDIATRIC Adverse Events Version 2.1,

July 2017

The Division of AIDS (DAIDS) oversees more than 300 clinical trials domestically and internationally, which evaluate the safety and efficacy of therapeutic products, vaccines, and other preventive modalities. Adverse event (AE) data collected during these clinical trials form the basis for subsequent safety and efficacy analyses of pharmaceutical products and medical devices. Incorrect and inconsistent AE severity grading can lead to inaccurate data analyses and interpretation, which in turn can impact the safety and well-being of clinical trial participants and future patients using pharmaceutical products.

Over the years, DAIDS scientific knowledge and experience have expanded, necessitating revisions of the DAIDS grading table which serves as a guide for assessing the severity of AEs (including clinical and laboratory abnormalities) in participants enrolled in DAIDS-sponsored and -supported clinical trials. The *Division of AIDS (DAIDS) Table for Grading the Severity of Adult and Pediatric Adverse Events, Corrected Version 2.1 (July 2017)* updates and replaces version 2.1 (March 2017).

Glossary/Definitions of terms used in tables:

AE	Adverse event; Any unfavorable and unintended sign (including an abnormal laboratory finding), symptom, or disease temporally associated with the use of a medical treatment or procedure regardless of whether it is considered related to the medical treatment or procedure.
ALT (SGPT)	Alanine aminotransferase (serum glutamic pyruvic transaminase)
ANC	Absolute neutrophil count
AST (SGOT)	Aspartate aminotransferase (serum glutamic-oxaloacetic transaminase)
AV	Atrioventricular
Basic Self-care Functions	Adult Activities such as bathing, dressing, toileting, transfer or movement, continence, and feeding. Young Children Activities that are age and culturally appropriate, such as feeding one's self with culturally appropriate eating implements.
BMI z-score	Body mass index z- score; A body reference norm. Specifically, the number of standard deviations a participant's BMI differs from the average BMI for their age, sex, and ethnicity.
BMD t-score	Bone mineral density t-score; The number of standard deviations above or below the mean bone mineral density of a healthy 30 year old adult of the same sex and ethnicity as the participant.
BMD z-score	Bone mineral density z-score; The number of standard deviations a participant's BMD differs from the average BMD for their age, sex, and ethnicity.

BPAP	Bilevel positive airway pressure; A mode used during noninvasive positive pressure ventilation.
Chemical Pregnancy	A pregnancy in which a positive pregnancy test is followed by a negative pregnancy test without evidence of a clinical pregnancy loss.
CNS	Central nervous system
CPAP	Continuous positive airway pressure
DAERS	DAIDS Adverse Experience Reporting System; An internet-based system developed for clinical research sites to report Expedited Adverse Events (EAEs) to DAIDS. It facilitates timely EAE report submission and serves as a centralized location for accessing and processing EAE information for reporting purposes.
Disability	A substantial disruption of a person's ability to conduct normal life functions.
ECG	Electrocardiogram
eGFR	Estimated glomerular filtration rate
Hospitalization	Does not include the following hospital admissions: under 24 hours, unrelated to an adverse event (e.g., for labor and delivery, cosmetic surgery, social or administrative for temporary placement [for lack of a place to sleep]), protocol-specified, and for diagnosis or therapy of a condition that existed before the receipt of a study agent and which has not increased in severity or frequency.
INR	International normalized ratio
Intervention	Medical, surgical, or other procedures recommended or provided by a healthcare professional for the treatment of an adverse event.
IV	Intravenous
IVIG	Intravenous immune globulin
LDL	Low density lipoprotein
LLN	Lower limit of normal
Life-threatening AE	Any adverse event that places the participant, in the view of the investigator, at immediate risk of death from the reaction when it occurred (i.e., it does not include a reaction that would have caused death if it had occurred in a more severe form).
NA	Not applicable
Participant ID	The identification number assigned to a study participant which is used to track study-related documentation, including any reported AEs.
PR Interval	The interval between the beginning of the P wave and the beginning of the QRS complex of an electrocardiogram that represents the time between the beginning of the contraction of the atria and the beginning of the contraction of the ventricles.
PT	Prothrombin time
PTT	Partial thromboplastin time
QTc Interval	The measure of time between the onset of ventricular depolarization and completion of ventricular repolarization corrected for ventricular rate.
RBC	Red blood cell
SI	Standard international unit
ULN	Upper limit of normal

Usual Social & Functional Activities	Activities which adults and children perform on a routine basis and those which are part of regular activities of daily living, for example:
	Adults
	Adaptive tasks and desirable activities, such as going to work, shopping, cooking, use of transportation, or pursuing a hobby.
	Young Children
	Activities that are age and culturally appropriate, such as social interactions, play activities, or learning tasks.
WBC	White blood cell
WHO	World Health Organization
WNL	Within normal limits

Instructions for use

The *Division of AIDS (DAIDS) Table for Grading the Severity of Adult and Pediatric Adverse Events, Version 2.1* consists of parameters, or AEs, with severity grading guidance that are to be used in DAIDS clinical trials for safety data reporting to maintain accuracy and consistency in the evaluation of AEs. The term “severe” is not the same as the term “serious” in classifying AEs. The severity of a specific event describes its intensity, and it is the intensity which is graded. Seriousness, which is not graded, relates to an outcome of an AE and is a regulatory definition.

Clinical sites are encouraged to report parameters in the DAIDS grading table as they are written to maintain data consistency across clinical trials. However, since some parameters can be reported with more specificity, clinical sites are encouraged to report parameters that convey additional clinical information. For example, diarrhea could be reported as neonatal diarrhea; seizures, as febrile seizures; and pain, as jaw pain.

General Considerations

The DAIDS grading table provides an AE severity grading scale ranging from grades 1 to 5 with descriptions for each AE based on the following general guidelines:

Grade 1 indicates a mild event

Grade 2 indicates a moderate event

Grade 3 indicates a severe event

Grade 4 indicates a potentially life-threatening event

Grade 5 indicates death (Note: This grade is not specifically listed on each page of the grading table).

Determining Severity Grade for Parameters “Between Grades”

If the severity of a clinical AE could fall under either one of two grades (e.g., the severity of an AE could be either Grade 2 or Grade 3), select the higher of the two grades for the AE. If a laboratory value that is graded as a multiple of the ULN or LLN falls between two grades, select the higher of the two grades for the AE. For example, Grade 1 is $2.5 \times$ ULN and Grade 2 is $2.6 \times$ ULN for a parameter. If the lab value is $2.53 \times$ ULN (which is between the two grades), the severity of this AE would be Grade 2, the higher of the two grades.

Values Below Grade 1

Any laboratory value that is between either the LLN or ULN and Grade 1 should not be graded.

Laboratory Values

General. An asymptomatic, abnormal laboratory finding without an accompanying AE should not be reported to DAIDS in an expedited timeframe unless it meets protocol-specific reporting requirements. Sites should refer to the applicable network standards for reporting abnormal laboratory findings on the clinical case report forms.

Values below Grade 1. Any laboratory value that is between the ULN and grade 1 (for high values) or the LLN and grade 1 (for low values) should not be graded or reported as an AE. Sites

should consult the *Manual for Expedited Reporting of Adverse Events to DAIDS, Version 2.0* and their protocol when making an assessment of the need to report an AE.

Overlap of Local Laboratory Normal Values with Grading Table Ranges. When local laboratory normal values fall within grading table laboratory ranges, the severity grading is based on the ranges in the grading table unless there is a protocol-specific grading criterion for the laboratory value. For example, "Magnesium, Low" has a grade 1 range of 1.2 to < 1.4 mEq/L, while a particular laboratory's normal range for magnesium may be 1.3 to 2.8 mEq/L. If a study participant's magnesium laboratory value is 1.3 mEq/L, the laboratory value should be graded as grade 1.

Estimating Severity Grade for Parameters Not Identified in the Grading Table

The functional table below should be used to grade the severity of an AE that is not specifically identified in the grading table. In addition, all deaths related to an AE are to be classified as grade 5.

PARAMETER	GRADE 1 MILD	GRADE 2 MODERATE	GRADE 3 SEVERE	GRADE 4 POTENTIALLY LIFE-THREATENING
Clinical adverse event NOT identified elsewhere in the grading table	Mild symptoms causing no or minimal interference with usual social & functional activities with intervention not indicated	Moderate symptoms causing greater than minimal interference with usual social & functional activities with intervention indicated	Severe symptoms causing inability to perform usual social & functional activities with intervention or hospitalization indicated	Potentially life-threatening symptoms causing inability to perform basic self-care functions with intervention indicated to prevent permanent impairment, persistent disability, or death

Major Clinical Conditions

Cardiovascular

PARAMETER	GRADE 1 MILD	GRADE 2 MODERATE	GRADE 3 SEVERE	GRADE 4 POTENTIALLY LIFE-THREATENING
Arrhythmia (by ECG or physical examination) Specify type, if applicable	No symptoms AND No intervention indicated	No symptoms AND Non-urgent intervention indicated	Non-life-threatening symptoms AND Non-urgent intervention indicated	Life-threatening arrhythmia OR Urgent intervention indicated
Blood Pressure Abnormalities ¹ Hypertension (with the lowest reading taken after repeat testing during a visit) ≥ 18 years of age	140 to < 160 mmHg systolic OR 90 to < 100 mmHg diastolic	≥ 160 to < 180 mmHg systolic OR ≥ 100 to < 110 mmHg diastolic	≥ 180 mmHg systolic OR ≥ 110 mmHg diastolic	Life-threatening consequences in a participant not previously diagnosed with hypertension (e.g., malignant hypertension) OR Hospitalization indicated
< 18 years of age	> 120/80 mmHg	≥ 95th to < 99th percentile + 5 mmHg adjusted for age, height, and gender (systolic and/or diastolic)	≥ 99th percentile + 5 mmHg adjusted for age, height, and gender (systolic and/or diastolic)	Life-threatening consequences in a participant not previously diagnosed with hypertension (e.g., malignant hypertension) OR Hospitalization indicated
Hypotension	No symptoms	Symptoms corrected with oral fluid replacement	Symptoms AND IV fluids indicated	Shock requiring use of vasopressors or mechanical assistance to maintain blood pressure
Cardiac Ischemia or Infarction Report only one	NA	NA	New symptoms with ischemia (stable angina) OR New testing consistent with ischemia	Unstable angina OR Acute myocardial infarction

¹ Blood pressure norms for children < 18 years of age can be found in: Expert Panel on Integrated Guidelines for Cardiovascular Health and Risk Reduction in Children and Adolescents. *Pediatrics* 2011;128:S213; originally published online November 14, 2011; DOI: 10.1542/peds.2009-2107C.

Heart Failure	No symptoms AND Laboratory or cardiac imaging abnormalities	Symptoms with mild to moderate activity or exertion	Symptoms at rest or with minimal activity or exertion (e.g., hypoxemia) OR Intervention indicated (e.g., oxygen)	Life-threatening consequences OR Urgent intervention indicated (e.g., vasoactive medications, ventricular assist device, heart transplant)
Hemorrhage (with significant acute blood loss)	NA	Symptoms AND No transfusion indicated	Symptoms AND Transfusion of \leq 2 units packed RBCs indicated	Life-threatening hypotension OR Transfusion of $>$ 2 units packed RBCs (for children, packed RBCs $>$ 10 cc/kg) indicated
Prolonged PR Interval or AV Block Report only one > 16 years of age	PR interval 0.21 to < 0.25 seconds	PR interval \geq 0.25 seconds OR Type I 2nd degree AV block	Type II 2nd degree AV block or ventricular delay of 3.0 seconds	Complete AV block
\leq 16 years of age	1st degree AV block (PR interval $>$ normal for age and rate)	Type I 2nd degree AV block	Type II 2nd degree AV block or ventricular delay of 3.0 seconds	Complete AV block
Prolonged QTc Interval ²	0.45 to 0.47 seconds	> 0.47 to 0.50 seconds	> 0.50 seconds OR \geq 0.06 seconds above baseline	Life-threatening consequences (e.g., Torsade de pointes, other associated serious ventricular dysrhythmia)
Thrombosis or Embolism Report only one	NA	Symptoms AND No intervention indicated	Symptoms AND Intervention indicated	Life-threatening embolic event (e.g., pulmonary embolism, thrombus)

² As per Bazett's formula.

Dermatologic

PARAMETER	GRADE 1 MILD	GRADE 2 MODERATE	GRADE 3 SEVERE	GRADE 4 POTENTIALLY LIFE-THREATENING
Alopecia (scalp only)	Detectable by study participant, caregiver, or physician AND Causing no or minimal interference with usual social & functional activities	Obvious on visual inspection AND Causing greater than minimal interference with usual social & functional activities	NA	NA
Bruising	Localized to one area	Localized to more than one area	Generalized	NA
Cellulitis	NA	Non-parenteral treatment indicated (e.g., oral antibiotics, antifungals, antivirals)	IV treatment indicated (e.g., IV antibiotics, antifungals, antivirals)	Life-threatening consequences (e.g., sepsis, tissue necrosis)
Hyperpigmentation	Slight or localized causing no or minimal interference with usual social & functional activities	Marked or generalized causing greater than minimal interference with usual social & functional activities	NA	NA
Hypopigmentation	Slight or localized causing no or minimal interference with usual social & functional activities	Marked or generalized causing greater than minimal interference with usual social & functional activities	NA	NA
Petechiae	Localized to one area	Localized to more than one area	Generalized	NA

Pruritus ³ (without skin lesions)	Itching causing no or minimal interference with usual social & functional activities	Itching causing greater than minimal interference with usual social & functional activities	Itching causing inability to perform usual social & functional activities	NA
Rash Specify type, if applicable	Localized rash	Diffuse rash OR Target lesions	Diffuse rash AND Vesicles or limited number of bullae or superficial ulcerations of mucous membrane limited to one site	Extensive or generalized bullous lesions OR Ulceration of mucous membrane involving two or more distinct mucosal sites OR Stevens-Johnson syndrome OR Toxic epidermal necrolysis

Endocrine and Metabolomic

PARAMETER	GRADE 1 MILD	GRADE 2 MODERATE	GRADE 3 SEVERE	GRADE 4 POTENTIALLY LIFE- THREATENING
Diabetes Mellitus	Controlled without medication	Controlled with medication OR Modification of current medication regimen	Uncontrolled despite treatment modification OR Hospitalization for immediate glucose control indicated	Life-threatening consequences (e.g., ketoacidosis, hyperosmolar nonketotic coma, end organ failure)
Gynecomastia	Detectable by study participant, caregiver, or physician AND Causing no or minimal interference with usual social & functional activities	Obvious on visual inspection AND Causing pain with greater than minimal interference with usual social & functional activities	Disfiguring changes AND Symptoms requiring intervention or causing inability to perform usual social & functional activities	NA
Hyperthyroidism	No symptoms AND Abnormal laboratory value	Symptoms causing greater than minimal interference with usual social & functional activities OR Thyroid suppression therapy indicated	Symptoms causing inability to perform usual social & functional activities OR Uncontrolled despite treatment modification	Life-threatening consequences (e.g., thyroid storm)

³ For pruritus associated with injections or infusions, see the *Site Reactions to Injections and Infusions* section (page 23).

Hypothyroidism	No symptoms AND Abnormal laboratory value	Symptoms causing greater than minimal interference with usual social & functional activities OR Thyroid replacement therapy indicated	Symptoms causing inability to perform usual social & functional activities OR Uncontrolled despite treatment modification	Life-threatening consequences (e.g., myxedema coma)
Lipoatrophy⁴	Detectable by study participant, caregiver, or physician AND Causing no or minimal interference with usual social & functional activities	Obvious on visual inspection AND Causing greater than minimal interference with usual social & functional activities	Disfiguring changes	NA
Lipohypertrophy⁵	Detectable by study participant, caregiver, or physician AND Causing no or minimal interference with usual social & functional activities	Obvious on visual inspection AND Causing greater than minimal interference with usual social & functional activities	Disfiguring changes	NA

Gastrointestinal

PARAMETER	GRADE 1 MILD	GRADE 2 MODERATE	GRADE 3 SEVERE	GRADE 4 POTENTIALLY LIFE-THREATENING

⁴ Definition: A disorder characterized by fat loss in the face, extremities, and buttocks.

⁵ Definition: A disorder characterized by abnormal fat accumulation on the back of the neck, breasts, and abdomen.

Anorexia	Loss of appetite without decreased oral intake	Loss of appetite associated with decreased oral intake without significant weight loss	Loss of appetite associated with significant weight loss	Life-threatening consequences OR Aggressive intervention indicated (e.g., tube feeding, total parenteral nutrition)
Ascites	No symptoms	Symptoms AND Intervention indicated (e.g., diuretics, therapeutic paracentesis)	Symptoms recur or persist despite intervention	Life-threatening consequences
